3.2 Study Schema

4. SUBJECT SELECTION

4.1 Inclusion Criteria

To be enrolled in the study, each potential subject must satisfy all of the following inclusion criteria:

- 1. Men and women \geq 18 years of age
- 2. Pathologically confirmed:
 - a) Phase 1b: diffuse large B-cell lymphoma or follicular lymphoma (grade 1, 2, or 3A) according to World Health Organization (WHO) criteria
 - b) Phase 2: diffuse large B-cell lymphoma or follicular lymphoma (grade 1, 2, or 3A) according to WHO criteria without clinical or pathological evidence of transformation
- 3. Provision of a fresh tumor biopsy or an available archival tumor sample processed as formalin-fixed, paraffin-embedded (FFPE) taken within 3 months of screening, and after the most recent treatment (Note: Earlier archived tumor tissue from all enrolled subjects will also be requested.)
- 4. Relapsed or refractory disease:
 - A. DLBCL
 - 1) Relapsed or refractory disease, defined as:
 - a) Recurrence of disease after a complete response (CR),

OR

- b) Partial response (PR), stable disease (SD) or progressive disease (PD) at completion of the treatment regimen preceding entry to the study (residual disease)
- 2) Subjects who have not already had a stem cell transplant must not be considered a candidate for high dose chemotherapy with stem cell transplant (HDT/SCT) and must meet at least one of the following criteria:
 - a) Age \geq 70 years
 - b) Diffuse lung capacity for carbon monoxide <50% by pulmonary function test
 - c) Left ventricular ejection fraction <50% by multiple gated acquisition / echocardiogram
 - d) Other organ dysfunction or co-morbidities precluding the use of HDT/SCT on the basis of unacceptable risk of treatment-related morbidity
 - e) Failure to achieve PR or CR with salvage therapy
 - f) Subject refusal of HDT/SCT

B. FL

- 1) Previously received at least one appropriate chemoimmunotherapy regimen and have relapsed or refractory disease
- 5. Measurable disease: One or more measurable disease sites on CT scan (>1.5 cm in longest dimension) is required. Lesions in anatomical locations (such as extremities or soft tissue lesions) that are not well visualized by CT may be measured by MRI instead.
- 6. Adequate hematologic function independent of transfusion support for at least 7 days prior to screening and independent of growth factor support for at least 14 days prior to screening, defined as:
 - Absolute neutrophil count >1500 cells/mm³ ($1.50 \times 10^{9}/L$)
 - Platelet count >50,000 cells/mm³ (50 x 10⁹/L) unless there is documented bone marrow involvement
 - Hemoglobin >8.0 g/dL
- 7. Adequate hepatic and renal function defined as:
 - Serum aspartate transaminase (AST) or alanine transaminase (ALT) ≤2.5 x upper limit of normal (ULN)
 - Bilirubin ≤1.5 x ULN (unless bilirubin rise is due to Gilbert's syndrome such that bilirubin ≤3 x ULN or is of non-hepatic origin)
 - Estimated Creatinine Clearance \geq 40 mL/min (Cockcroft-Gault)
- 8. Prothrombin time (PT) <1.5 x ULN and activated partial thromboplastin time (aPTT) <1.5 x ULN
- 9. Eastern Cooperative Oncology Group (ECOG) performance status of 0 or 1
- 10. Female subjects must either be of non-reproductive potential (ie, post-menopausal by history: ≥60 years old and no menses for ≥1 year without an alternative medical cause; OR history of hysterectomy, OR history of bilateral tubal ligation; OR history of bilateral oophorectomy) or must have a negative serum pregnancy test upon study entry.
- 11. Male subjects who are not sterilized and who are sexually active with a female partner of childbearing potential, and female subjects of childbearing potential who are sexually active with a nonsterilized male partner must agree to use 2 highly effective methods of birth control (eg, condoms, implants, injectables, combined oral contraceptives, or intrauterine devices [IUDs]) during the period of therapy and for 3 months after the last dose of study drug (see Appendix 7).
- 12. Male subjects must agree to not donate sperm, and female subjects must agree to not donate eggs (ova, oocytes) for the purposes of assisted reproduction during or for 3 months after the last dose of either study drug.

4.2 Exclusion Criteria

To be enrolled in the study, potential subjects must meet NONE of the following exclusion criteria:

- 1. Anti-tumor therapy (chemotherapy, antibody therapy, immunotherapy, biologic-based therapy, or investigational agent) within 14 days of study Day 1 (or six weeks for nitrosureas or mitomycin C); Enrollment of subjects that have received molecularly-targeted small molecule inhibitors less than 28 days prior to study Day 1 will be permitted if more than 14 days and at least 5 drug half-lives have passed prior to receiving the first dose of ibrutinib.
- 2. Prior therapy with ibrutinib or other BTK inhibitor and/or anti-PD1, anti-PD-L1, anti-PD-L2, anti-CD137, or anti-cytotoxic T-lymphocyte associated antigen 4 (CTLA-4) antibody
- 3. Unresolved toxicities from prior anti-cancer therapy, defined as having not resolved to Common Terminology Criteria for Adverse Event (CTCAE, version 4.03) grade 0 or 1, or to the levels dictated in the inclusion/exclusion criteria with the exception of stable neuropathy, vitiligo, alopecia, or other irreversible toxicity not reasonably expected to be exacerbated by study treatment (eg, hearing loss)
- 4. Treatment with a strong cytochrome P450 (CYP) 3A inhibitor (see Appendix 4)
- 5. Vaccinated with live, attenuated vaccines within 4 weeks of first dose of study drug (Note: Subjects, if enrolled, should not receive live vaccines during the study and until 30 days after the last dose of study drug)
- 6. Current or prior use of immunosuppressive medication within 14 days before the first dose of MEDI4736. The following are exceptions to this criterion:
 - Intranasal, inhaled, topical corticosteroids, or local corticosteroid injections (eg, intraarticular injection)
 - Systemic corticosteroids at doses not to exceed 10 mg/day of prednisone or its equivalent
 - Corticosteroids as pre-medication for hypersensitivity reactions (eg, CT scan premedication)
- 7. History of allogeneic organ transplant or <100 days after autologous transplant
- 8. Primary CNS lymphoma or evidence of CNS involvement by lymphoma
- 9. Any uncontrolled active systemic infection, or recent infection requiring intravenous antibiotic treatment that was completed ≤14 days before the first dose of study drug
- 10. Known history of previous clinical diagnosis of active tuberculosis
- 11. Known bleeding disorders (eg, von Willebrand's disease or hemophilia)
- 12. History of stroke or intracranial hemorrhage within 6 months prior to enrollment
- 13. Major surgery within 4 weeks of first dose of study drug
- 14. Concomitant use of warfarin or other Vitamin K antagonists
- 15. History of primary immunodeficiency

- 16. Known history of human immunodeficiency virus (HIV) or current chronic/active infection with hepatitis C virus (HCV) or hepatitis B virus (HBV)
 - Subjects with chronic or active hepatitis B as diagnosed by serologic tests are excluded from the study. In equivocal cases, hepatitis B or C polymerase chain reaction (PCR) may be performed and must be negative for enrollment.
- 17. Currently active, clinically significant cardiovascular disease, such as uncontrolled arrhythmia or Class 3 or 4 congestive heart failure as defined by the New York Heart Association Functional Classification (see Appendix 6); or a history of myocardial infarction, uncontrolled hypertension or cardiac arrhythmia, unstable angina, or acute coronary syndrome within 6 months prior to enrollment
- 18. Mean QT interval corrected for heart rate (QTc) ≥470 ms calculated from 3 electrocardiograms (ECGs) using Fridericia formula
- 19. Unable to swallow capsules or malabsorption syndrome, disease or condition significantly affecting gastrointestinal function, or resection of the stomach or small bowel, or partial or complete bowel obstruction
- 20. Lactating women, men planning to father a child, or women planning pregnancy while taking study drug or within 3 months after the last dose of study drug
- 21. Known allergy or hypersensitivity to ibrutinib or MEDI4736 or any excipient
- 22. Active or prior documented autoimmune or inflammatory disorders including but not limited to inflammatory bowel disease (eg, colitis, Crohn's disease), diverticulitis with the exception of a prior resolved episode or diverticulosis, celiac disease, irritable bowel disease, or other serious gastrointestinal chronic conditions associated with diarrhea, type I diabetes mellitus, multiple sclerosis, systemic lupus erythematosus, Wegener's granulomatosis (granulomatosis with polyangiitis), myasthenia gravis, Graves' disease, rheumatoid arthritis, pneumonitis, interstitial lung disease, hypophysitis, or uveitis within the past 3 years prior to the start of treatment. The following are exceptions to this criterion:
 - Subjects with vitiligo or alopecia
 - Subjects with hypothyroidism (eg, following Hashimoto syndrome) stable on hormone replacement or psoriasis not requiring systemic treatment
- 23. History of other malignancies, except
 - Malignancy treated with curative intent and with no known active disease present for ≥5 years before the first dose of study drug and felt to be at low risk for recurrence by the treating physician
 - Adequately treated non-melanoma skin cancer or lentigo maligna without evidence of disease
 - Adequately treated carcinoma in situ without evidence of disease
- 24. Unwilling or unable to participate in all required study evaluations and procedures
- 25. Any life-threatening illness, medical condition, or organ system dysfunction that, in the investigator's opinion, could compromise the subject's safety or put the study outcomes at

undue risk, eg, psychiatric illness/social situations that would limit compliance with study requirement or compromise the ability of the subject to give written informed consent

- 26. Unable to understand the purpose and risks of the study and to provide a signed and dated informed consent form (ICF) and authorization to use protected health information (in accordance with national and local subject privacy regulations)
- 27. Concurrent enrollment in another clinical study, unless in a follow-up period or in an observational study

5. TREATMENT OF SUBJECTS

5.1 Treatment Allocation

This is an open-label study (both Phase 1b and Phase 2). After the subject has completed all baseline (screening) procedures and meets the inclusion and none of the exclusion criteria, study site personnel can enroll the subject. All enrolled subjects will receive open-label ibrutinib capsules and MEDI4736 intravenous infusions.

In Phase 1b, two dose levels of ibrutinib (560 or 420 mg/day) and MEDI4736 (10 or 3 mg/kg IV every 2 weeks) may be tested (Table 2). The starting dose will be 560 mg of ibrutinib PO daily and 10 mg/kg of MEDI4736 IV every 2 weeks. The dose may be modified based on the number of DLTs observed. In each cohort, a sentinel subject will have a 3-day observation period prior to dosing of subsequent subjects to monitor for unexpected toxicities. In Phase 2, subjects will be treated at the RP2D as determined in Phase 1b.

5.2 Phase 1b Dose De-escalation and Stopping Rules

Refer to Figure 1 for a summary of the de-escalation process.

Phase 1b will follow a 6+3 design with 6-9 subjects at each dose level. Before determining the RP2D, 6 subjects in any given cohort must have completed the DLT observation period which is defined as the assessment period from Day 1 of Cycle 1 of the combination therapy until the laboratory evaluations on Day 1 of Cycle 2 which will occur before the MEDI4736 infusion on Day 1 of Cycle 2. The dose will be selected as the RP2D if the subject incidence of DLTs during the DLT assessment period with combination study treatment is <33% (ie, $\leq 1/6$ or $\leq 2/9$ subjects with a DLT). If there are ≥ 3 subjects with a DLT in Cohort 1, then the next lower dose level (Cohorts -1A and -1B, see Table 2) will be enrolled.

Cohort -1A and -1B are two parallel dose de-escalation cohorts and will be enrolled concurrently in a non-randomized fashion in the sequence of -1A followed by -1B. For example, the first available subject will go to Cohort -1A, the second subject to Cohort -1B, the third to -1A, the fourth to -1B, etc. However, when one dose de-escalation cohort needs an additional 3 subjects to evaluate DLTs, all available subjects will be assigned to this cohort first. In these cohorts, it will be determined which dosing schedule is most appropriate for the Phase 2 portion of the study. Determination will be based on the safety profile of the 2 treatment regimens, as evaluated by the Sponsor and enrolling investigators, potentially taking PK and pharmacodynamic aspects into consideration (see Section 12.11).

If the subject incidence of DLTs within the DLT assessment period with combination study treatment is <33.3% (ie, ≤1 of 6 or ≤2 of 9 subjects with a DLT), this dose level will be considered safe to proceed to Phase 2, and thus will be defined as the RP2D.

Enrollment in Cohort 1 will proceed as follows:

- If 0 or 1 DLT is observed during the DLT observation period in the initial 6 subjects in Cohort 1, then this dose will be the RP2D.
- If 2 DLTs are observed in the initial 6 subjects in Cohort 1, then 3 additional subjects will be enrolled to this cohort.
 - If 0 DLT in the 3 additional subjects is observed, then this dose will be the RP2D.
 - If 1 or more DLT is observed, the dose will be de-escalated to Cohorts -1A and -1B
- If 3 or more DLTs are observed in the initial 6 subjects, enrollment into Cohort 1 will be stopped and the dose will be de-escalated to Cohorts -1A and -1B.

A similar 6+3 cohort design will be utilized in the dose de-escalation cohorts. If necessary, the dose de-escalation cohort -2 will be enrolled thereafter.

If a subject experiences a DLT during the DLT observation period, the subject will discontinue treatment. However, any subject(s) tolerating the dose level through the DLT observation period will continue with the same dose level of study drug even if subsequently-enrolled study subjects receive treatment at a dose de-escalation.

A Dose Level Review Committee (DLRC) will evaluate the safety data from each cohort of Phase 1b. Members of this committee will include participating investigators or designees as well as the Sponsor (invitees include: the Medical Monitor or designee, the clinical lead, a Drug Safety representative and a Biostatistician) (see Section 12.11).

5.3 Definition of Dose-Limiting Toxicity (DLT)

The assessment of DLT will follow the guidelines provided in the Common Terminology Criteria for Adverse Events (CTCAE) version 4.03 (accessible at the website, http://evs.nci.nih.gov/ftp1/CTCAE/CTCAE_4.03_2010-06-14_QuickReference_8.5x11.pdf). The Phase 1b DLT observation period will occur from Day 1 of Cycle 1 of ibrutinib in combination with MEDI4736 treatment to the laboratory evaluations on Day 1 of Cycle 2 which will occur before the MEDI4736 infusion on Day 1 of Cycle 2.

A DLT is an AE at least possibly related to study drug(s) defined as:

- 1) Any Grade 3 or higher non-hematologic AE (with additional clarifications below)
 - Grade 3 or higher nausea, vomiting, or diarrhea (non-colitis-related) that is uncontrolled by maximal supportive care and persists for >7 days would be considered a DLT
 - Grade 3 fatigue that persists for >7 days would be considered a DLT
 - Any Grade 3 immune-related adverse event (irAE) that does not downgrade to Grade ≤2 within 3 days after onset of the event despite maximal supportive care including systemic corticosteroids, or does not downgrade to Grade ≤1 or baseline within 14 days would be considered a DLT

- Any Grade ≥ 2 pneumonitis that does not resolve to Grade ≤ 1 within 3 days of the initiation of maximal supportive care would be considered a DLT.
- The DLT definition excludes the following conditions:
 - Grade 3 endocrinopathy that is managed with or without systemic corticosteroid therapy and/or hormone replacement therapy and the subject is asymptomatic
 - Grade 3 inflammatory reaction attributed to a local antitumor response (eg, inflammatory reaction at sites of metastatic disease, lymph nodes, etc)
 - Vitiligo or alopecia of any AE grade would not be considered a DLT
- 2) Clinically relevant hematologic AE such as:
 - Grade 3 or 4 neutropenia (ANC<1,000/ mm³) lasting >7 days
 - Febrile neutropenia (Grade 3 or 4 neutropenia with fever \geq 38.3°C)
 - Grade 3 or 4 thrombocytopenia (<25,000/ mm³) lasting >7 days or requiring transfusion or associated with Grade ≥2 bleeding
 - Any other Grade 4 hematologic AE, except lymphopenia

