5.4 Replacement of Subjects

During the Phase 1b DLT observation period, subjects will be replaced for any of the following reasons:

- Missed \geq 5 consecutive doses of ibrutinib or missed 7 total doses (not due to DLT)
- Missed dose of MEDI4736 or received the MEDI4736 dose outside of the protocolallowed window (±2 days) (not due to DLT)
- Study drug discontinuation for any reason other than DLT

Subjects who are replaced for missed doses may continue to receive study treatment if there is a clinical benefit, but they will not be part of the DLT analysis.

During the Phase 2 portion of the study, if a subject discontinues study drug prior to the first tumor response assessment for reasons other than progressive disease, the subject may be replaced.

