	Grade 1	No dose modification	 For Grade 1: Close monitoring for worsening symptoms Consider symptomatic treatment including hydration, electrolyte replacement, dietary changes (eg, American Dietetic Association colitis diet), and loperamide
	Grade 2	 Hold study drug/study regimen until resolution to Grade ≤1 If toxicity worsens then treat as Grade 3 or Grade 4 If toxicity improves to baseline then treat at next scheduled treatment date 	 For Grade 2: Consider symptomatic treatment including hydration, electrolyte replacement, dietary changes (eg, American Dietetic Association colitis diet), and loperamide and/or budesonide If event is persistent (>3-5 days) or worsens, consider prednisone 0.5 to 1 mg/kg/day or IV equivalent If not responsive within 3-5 days, consider IV corticosteroids (eg, methylprednisolone IV or equivalent) at 1 to 2 mg/kg/day If event is not responsive within 3-5 days or worsens, additional workup and treatment with IV methylprednisolone 2-4 mg/kg/day should be considered If no improvement within 3-5 days, further immunosuppressives (eg, infliximab) should be considered Consult study physician if no resolution to Grade ≤1 in 3-4 days Once improving, gradually taper steroids over ≥4 weeks
	Grade 3 or 4	Permanently discontinue study drug/study regimen	 For Grade 3 or 4: Discuss with study physician Monitor stool frequency and volume and maintain hydration Urgent GI consult and imaging as appropriate Initiate empiric IV corticosteroids (eg, methylprednisolone IV or equivalent) at 1 to 4 mg/kg/day If no improvement within 3-5 days, consider further immunosuppressives (eg, infliximab) Caution: Ensure GI consult to rule out bowel perforation and refer to label before using

Immune-Mediated Reactions			
	Dose Modifications	Toxicity Management	
		infliximab. Once improving, gradually taper steroids over ≥4 weeks and consider prophylactic antibiotics	
Hepatitis	Any Grade	 Monitor and evaluate liver function test: AST, ALT, ALP and total bilirubin Evaluate for alternative etiologies (eg, viral hepatitis, disease progression, concomitant medications) 	
	Grade 1 No dose modification If it worsens, treat as Grade 2 event	- Continue LFT monitoring per protocol	

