			_	Subjects should be evaluated to rule out any alternative etiology (eg, disease progression, infections, metabolic syndromes and medications, etc.). It should be noted that the diagnosis of immune-mediated peripheral neuromotor syndromes can be particularly challenging in subjects with underlying cancer, due to the multiple potential confounding effects of cancer (and its treatments) throughout the neuraxis. Given the importance of prompt and accurate diagnosis, it is essential to have a low threshold to obtain a neurological consult Neurophysiologic diagnostic testing (eg, electromyogram and nerve conduction investigations, and "repetitive stimulation" if myasthenia is suspected) are routinely indicated upon suspicion of such conditions and may be best facilitated by means of a neurology consultation Important to consider that the use of steroids as the primary treatment of Guillain-Barre is not typically considered effective. Subjects
				requiring treatment should be considered for plasmapharesis (or IVIgG, as an alternative)
	Grade 1	No dose modification	-	Discuss with the study physician Care should be taken to monitor subjects for sentinel symptoms of a potential decompensation as described above Consider a neurology consult unless the symptoms are very minor and stable
	Grade 2	Hold study drug/study regimen dose until resolution to Grade ≤ 1 Permanently discontinue study drug/study regimen if does not resolve to Grade ≤ 1 within 30 days or if there are	Gra - -	ade 2 : Moderate Discuss with the study physician Care should be taken to monitor subjects for sentinel symptoms of a potential decompensation as described above Obtain a Neurology Consult

Immune-Mediated Reactions		
	Dose Modifications	Toxicity Management
	signs of respiratory insufficiency or autonomic instability	 Sensory neuropathy/neuropathic pain may be managed by appropriate medications (eg, gabapentin, duloxetine, etc.) MYASTHENIA GRAVIS:
		 Steroids may be successfully used to treat Myasthenia Gravis. Important to consider that steroid therapy (especially with high doses) may result in transient worsening of myasthenia and should typically be administered in a monitored setting under supervision of a consulting neurologist.
		 Subjects unable to tolerate steroids may be candidates for treatment with plasmapharesis or IVIgG. Such decisions are best made in consultation with a neurologist, taking into account the unique needs of each subject.

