11.4.6.2. Pneumonitis

Pneumonitis has been reported in association with use of anti-PD-L1/anti-PD-1 antibodies (Brahmer 2012). Initial work-up should include a high-resolution CT scan, ruling out infection, and pulse oximetry. Additional assessments are to include pulmonary function tests and blood gases. Pulmonary consultation is recommended.

For Grade 2 pneumonitis that does not resolve to <Grade 1 within 3 days of maximal supportive care (including corticosteroids) or \geq Grade 3 pneumonitis, permanently discontinue MEDI4736.

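### On the reading that gives its time limits effect, Section 5.3 leaves some treatment-ending immune toxicities out of the DLT count that sets the RP2D

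*Protocol*

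**What the plan says.** Protocol Section 5.3 starts from related non-hematologic events of Grade 3 or higher and adds clarifications. One covers immune-related events: "Any Grade 3 immune-related adverse event (irAE) that does not downgrade to Grade ≤2 within 3 days after onset of the event" despite maximal care, or failure to reach Grade 1 or baseline within 14 days. Another covers gastrointestinal events: "Grade 3 or higher nausea, vomiting, or diarrhea (non-colitis-related) that is uncontrolled by maximal supportive care and persists for >7 days". The only Grade 2 non-hematologic event named is pneumonitis that does not settle within 3 days of maximal care.

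Table 4 (Section 5.6.2.5) says when to stop. For Grade 3 or 4 in its Diarrhea/Enterocolitis row, under the immune-mediated heading, the action is "Permanently discontinue study drug/study regimen", with no exception for recovery. For a Grade 2 peripheral neuromotor syndrome it calls for a permanent stop if the event has not resolved within 30 days or if there are "signs of respiratory insufficiency or autonomic instability".

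Section 5.2 links the two in one direction only: "If a subject experiences a DLT during the DLT observation period, the subject will discontinue treatment". Section 5.4 replaces a subject during the DLT window for "Study drug discontinuation for any reason other than DLT", and SAP 2.1 leaves anyone who meets a replacement criterion out of the DLT-evaluable set. At no more than 1 DLT in 6 or 2 in 9, Section 5.2 says "this dose level will be considered safe to proceed to Phase 2, and thus will be defined as the RP2D".

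**The concern.** Every DLT ends treatment, but not every toxicity for which the protocol ends treatment is a DLT. Excusing a short Grade 3 event makes sense when dosing can resume. For immune enterocolitis, Table 4 says it cannot. A subject could therefore stop permanently for a related toxicity, be replaced, and leave no trace in the count that fixes the Phase 2 dose.

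Section 1.3.5 reports no clinical data on the combination in FL or DLBCL, and Section 1.4.3 lists enterocolitis as an important potential risk of MEDI4736. The selected dose then goes to about 73 Phase 2 subjects (including any treated at that dose in Phase 1b). The Dose Level Review Committee sees each cohort's safety data, but no text tells it to count these stops or to depart from the rule.

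**Working it through.** **Step 1. The plan's own threshold.** 1/6 = 16.7% and 2/9 = 22.2% are below 33.3%; 2/6 and 3/9 equal 33.3% and are not. Phase 1b size runs from 1 × 6 = 6 to 4 × 9 = 36. Both agree with the protocol.

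**Step 2. Section 5.3 beside the stopping text.**

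| Related event in the DLT window | Stopping text | DLT under 5.3? |
|---|---|---|
| Grade 3 immune enterocolitis, Grade ≤2 within 3 days and Grade ≤1 or baseline within 14 days | Permanent stop (Table 4) | No, if the time limits have effect |
| Grade 3 hepatitis, transaminases >8 × ULN or bilirubin >5 × ULN, same recovery | Discontinue, no recovery route (Table 4) | No, on the same reading |
| Grade 2 neuromotor syndrome with respiratory or autonomic signs | Permanent stop (Table 4) | No, on any reading, unless the signs are reported separately as a related Grade ≥3 AE |
| Grade ≥3 pneumonitis | "Grade 3 pneumonitis, permanently discontinue MEDI4736" (Section 11.4.6.2) | Unclear: the bullet starts at Grade 2 and may only extend the definition downward |
| Grade 3 diarrhea, not immune-mediated | Hold and resume if recovered (Table 4 non-immune section), or Table 3 restart | Only if uncontrolled for >7 days; consistent with the stopping text |

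The last row is not a gap. If the diarrhea is judged immune-mediated, it falls under the irAE bullet and becomes the first row.

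**Step 3. One cohort.** Of the first 6 treated, 1 has a DLT and 1 stops for recovered Grade 3 immune enterocolitis. The second is replaced. If the replacement has no DLT, the count is 1/6 and the dose is the RP2D. Had the stop been counted, it would be 2/6, and 3 more subjects would be enrolled first.

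**Step 4. Size.** Let d be the DLT rate under 5.3 and t the rate of uncounted stops in the window. The documents give neither; d = 15% and t = 0.5% to 2% are assumptions.

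Pass probability: A(p) = P(X ≤ 1 | 6, p) + P(X = 2 | 6, p) × (1 − p)³.

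- Plan, subject replaced: p = d/(1 − t).
- Stops counted as DLTs: p = d + t.

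At t = 2%:
- Plan: p = 0.15/0.98 = 0.1531. A = 0.3691 + 0.4002 + 0.1808 × 0.6075 = 0.879.
- Counted: p = 0.17. A = 0.3269 + 0.4018 + 0.2057 × 0.5718 = 0.846.

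| t | Plan | Counted | Difference (points) |
|---|---|---|---|
| 0.5% | 88.3% | 87.6% | 0.8 |
| 1% | 88.2% | 86.6% | 1.6 |
| 1.5% | 88.1% | 85.6% | 2.4 |
| 2% | 87.9% | 84.6% | 3.3 |

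Differences are taken before rounding. With other DLT rates at t = 1%: 95.6% v 94.6% for d = 10%, and 77.7% v 75.8% for d = 20%.

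The probability of the Step 3 sequence is 30·d·t·(1 − d − t)⁴·(1 − d/(1 − t)). At d = 15% this is 1.0% for t = 0.5% and 3.6% for t = 2%.

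**The case against.** The strongest reply is textual. The lead line of 5.3 covers any Grade 3 or higher non-hematologic AE, the bullets are called clarifications, and true carve-outs have their own list, where recovered colitis does not appear. Read literally, recovered Grade 3 enterocolitis is already a DLT. But the irAE bullet starts at Grade 3, so its 3-day and 14-day limits would then do nothing. The literal reading is possible, which is why the point is conditional for enterocolitis and hepatitis. It does not reach the Grade 2 neuromotor syndrome.

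Table 4 is offered as guidance for clinical judgment, and separating a stop for one patient from a limit on the dose is a legitimate design choice. Both stand. They weigh against making DLT status depend on whether the investigator stops treatment. They do not explain why the protocol's own stopping text and its dose rule should part without saying so.

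It is also fair that the neuromotor case is remote, that these subjects remain in the safety population, and that the committee reviews them.

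A reader might infer that replacement itself loosens the rule. It does not: keeping such subjects as non-DLT would give a pass probability of 88.5%, against 88.3% when they are replaced (t = 0.5%). The gap lies in the definition.

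**Conclusion.** The point holds in limited form. On the reading that gives its time limits effect, 5.3 omits promptly recovered Grade 3 immune enterocolitis, which Table 4 stops permanently. On any reading it omits the Grade 2 neuromotor syndrome itself. The rule can then define an RP2D without counting that stop.

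The size is small: 0.8 to 3.3 points of pass probability at the assumed d = 15% and t = 0.5% to 2%, with subjects independent.

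Two stronger readings are not supported.

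- That the documents show how often this happens. The 0.1–1.5% for ibrutinib in Section 1.3.4.4 is Grade 3 gastrointestinal events, which Table 3 lets restart. The 2 MEDI4736 discontinuations for transaminase increases in Section 1.4.3 are not stated to be drug-related or to meet the hepatitis thresholds. Neither measures t.
- That an RP2D would plausibly be declared with a third of subjects stopped. One DLT in 6 evaluable plus 2 replaced would be 3/8 = 37.5%, above the limit. At d = 15%, the chance of declaring an RP2D with at least one third of treated subjects having a DLT or such a stop is 0.03% at t = 0.5% and 0.51% at t = 2%.

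This is an inexpensive improvement to consider, not a flaw that undermines the dose-finding.

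**What to change.** In Section 5.3, name the following as DLTs regardless of recovery when at least possibly related, keeping the listed exclusions:

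- Grade ≥3 immune-mediated enterocolitis
- Grade ≥3 pneumonitis
- Grade 3 hepatitis with transaminases >8 × ULN or bilirubin >5 × ULN, or meeting Hy's law
- Grade ≥2 peripheral neuromotor syndrome with respiratory insufficiency or autonomic instability

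Define them by the event, not by whether the investigator discontinues, so that identical events count alike across sites. Repeat the wording in the synopsis and SAP 1.1, which restate the definition. In Section 10.4.1 and SAP 2.1, state that a subject with a DLT is evaluable and not replaced. Before each RP2D decision, give the Dose Level Review Committee a list of any other related discontinuations in the cohort.

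The cost is a wording amendment with ethics approval and one short list per cohort, with no new visits or data. The downside is a slightly more conservative rule: besides the lower pass probability, at d = 15% the chance of expanding to 9 subjects rises from 17.7% to 18.4% at t = 0.5% and from 18.1% to 20.6% at t = 2%.
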